9.1.5 Death

Death must be considered an outcome of an AE and not an independent AE. The event or condition that caused the death must be recorded as the AE with the outcome of

death. If the cause of death is unknown and cannot be ascertained at the time of reporting, then the event must be reported as a “death NOS”. If the cause of death later becomes available (e.g., after autopsy), “death NOS” must be updated by the established cause of death.

9.1.6 Pre-existing Medical Conditions

A pre-existing medical condition is one that is present during the pre-treatment screening assessments. These conditions must be noted as medical history as described in [Section 6.2.1](#). Pre-existing medical conditions are not considered AEs unless any of the following characteristics worsen following initiation of any study-related procedure:

- Frequency
- Severity
- Character

If any of the above conditions apply, then this must be recorded as an AE. Convey that this is a change in a preexisting condition when describing the event.

9.1.7 Expectedness

The expectedness of the AE will be determined by the investigator based on current literature and the investigator’s experience. The most common AE associated with genistein supplementation is grade 2 abdominal pain ([Section 5.1.7](#)).

SAEs will also take into consideration the expectedness of an AE within the study population, due to the underlying anti-neoplastic treatment regimen and/or underlying disease.

See [Sections 9.2.1](#) and [9.2.2](#) for information on expectedness as it relates to required reporting.

9.1.8 Severity

The descriptions and grading scales found in the revised CTCAE version 4.0, dated 28May2009, will be utilized for AE reporting. All appropriate treatment areas should have access to a copy of the CTCAE version 4.0. A copy of the CTCAE version 4.0 can be downloaded from the CTEP website (<http://ctep.cancer.gov>, [Appendix A](#)).

To assess severity of AEs not included in the CTCAE version 4.0, use Table 2 below.

Table 4. AE Grading Scale for AEs Not Specifically Listed in the NCI CTCAE

Grade	Severity
1	Mild; asymptomatic or mild symptoms; clinical or diagnostic observations only; intervention not indicated.
2	Moderate; minimal, local or noninvasive intervention indicated; limiting age-appropriate instrumental ADL ^a
3	Severe or medically significant but not immediately life-threatening; hospitalization or

	prolongation of hospitalization indicated; disabling; limiting self-care ADL ^b
4	Life-threatening consequences; urgent intervention indicated.
5	Death related to AE
^a Instrumental activities of daily living (ADL) refers to preparing meals, shopping for groceries or clothes, using the telephone, managing money, etc. ^b Self-care ADL refers to bathing, dressing and undressing, feeding self, using the toilet, taking medications, and not bedridden.	

9.1.9 Serious Adverse Event [72]

A serious adverse event or experience (SAE) or serious adverse drug reaction (ADR) is any AE temporally associated with the subject's participation in research that meets any of the following criteria:

- Fatal
- Life-threatening (places the subject at immediate risk of death from the event as it occurred)
- Requires in-patient hospitalization or prolongation of existing hospitalization*
- Results in a congenital anomaly/birth defect
- Results in a persistent or significant disability/incapacity
- Important medical events that may not result in death, be life-threatening, or require hospitalization may be considered a serious adverse drug experience when, based upon appropriate medical judgment, they may jeopardize the subject safety and may require medical or surgical intervention to prevent one of the outcomes listed in the definition.

For reporting purposes, also consider the occurrences of pregnancy as an event which must be reported as an important medical event.

*Hospitalization or prolonged hospitalization must be documented and reported as a SAE, except if the hospitalization meets at least one of the following criteria:

- The hospitalization is less than 24 hours and without an admission
- Hospitalization for respite care
- Planned hospitalization required for or related to anti-neoplastic treatment (e.g. for anticipated procedures such as administration of chemotherapy, central line insertion, metastasis interventional therapy, resection of primary tumor, or elective surgery)
- Hospitalization for a pre-existing condition, provided that all of the following criteria are met:
 - The hospitalization was planned prior to the study or was scheduled during the study when elective surgery became necessary because of the expected normal progression of the disease.
 - The subject has not suffered a causative AE.

If the hospitalization meets any of these criteria, then it is not considered a SAE.

SAEs are subject to both expedited and routine reporting. See [Section 9.2.3.2](#) and the Procedure Manual for additional information on expedited reporting requirements for SAEs.

DRAFT

9.1.10 Attribution Assessment

The investigator will evaluate all AEs and to assess the attribution, if any, to study supplement. The following criteria will define the attribution [72]:

Definite: The AE *is clearly related* to the investigational intervention

Probable: The AE *is likely related* to the investigational intervention

Possible: The AE *may be related* to the investigational intervention

Unlikely: The AE *is doubtfully related* to the investigational intervention

Unrelated: The AE *is clearly NOT related* to the investigational intervention

9.2 Required Reporting

9.2.1 UVa Cancer Center DSMC Reporting Requirements

All AEs must be reported into UVa Cancer Center OnCore database within the time frame specified below. All timeframes are expressed in (calendar) days from the first point at which any member of the study team learned of the event.

For the purposes of reporting AEs for DSMC review, expectedness is defined in relationship to treatment with the investigational agent. I.e. Is the AE in question expected when undergoing genistein treatment? See Sections [5.1.7](#) and [5.2.4](#) for the expected AE. AEs meeting the thresholds below require additional reporting in OnCore beyond the routine data capture associated with a reporting period.

Target AEs do not need to be reported apart from routine data capture unless they meet the criteria below. Progressions, recurrences, and secondary malignancies must be reported within 30 days of the end of the reporting period during which they occurred, or the next quarterly deadline, whichever comes last. See the Procedure Manual for additional information pertaining to data capture.

Table 5. DSMC reporting requirements for AEs that occur during Cycles 1 – 4

Attribution to Study Supplement	Grades 1 & 2		Grade 3		Grade 4	Grade 5
	Expected & Unexpected		Expected & Unexpected		Unexpected	Unexpected
	Target AEs ¹	All other:	Target AEs ¹	All other:		
Unrelated	OnCore: 30 days/quarterly ³	Not required	OnCore: 30 days/quarterly ³	Not required	OnCore: 30 days/quarterly ³	See SAE
Unlikely				OnCore: 30 days from end of Cycle		
Possible				OnCore: 15 days from end of Cycle		
Probable						
Definite						
SAE ⁴	OnCore: (24-hrs), 7 days ²					

¹ Target AEs: Neutrophil count decreased, infection (any), mucositis oral, febrile neutropenia, fever, tinnitus & hearing impaired (subjects on platinum-based chemotherapy only), peripheral

motor neuropathy (subjects on vincristine only).
² Enter into Cancer Center database within 24 hours and submit supporting documentation within 7 days.
³ Data to be entered within 30 days of the end of the reporting period or the next quarterly deadline, whichever comes last. Deadlines are Jan. 31, Apr. 31, July 31, and Oct. 31.
⁴ Any AE that is an SAE must be reported using the SAE timeline regardless of grade or attribution.

Less stringent reporting is required during the follow-up period.

Table 6. DSMC reporting requirements for AEs that occur after the subject’s last cycle taking the study supplement until 6 months post-treatment (i.e. follow-up)

Attribution to Study Supplement	Grades 1 & 2	Grade 3	Grade 4	Grade 5
	Expected & Unexpected	Expected & Unexpected	Unexpected	Unexpected
Unrelated Unlikely	Not required	Not required	OnCore: 30 days/quarterly ²	See SAE
Possible Probable Definite		OnCore: 30 days from end of Reporting Period ³	OnCore: 15 days from end of Reporting Period ³	
SAE ⁴	OnCore: (24-hrs), 7 days ¹			

¹ Enter into Cancer Center database within 24 hours and submit supporting documentation within 7 days.
² Data to be entered within 30 days of the end of the reporting period or the next quarterly deadline, whichever comes last. Deadlines are Jan. 31, Apr. 31, July 31, and Oct. 31.
³ Reporting is not required if AE onset is > 30 days after the last dose of study supplement
⁴ Any AE that is an SAE must be reported using the SAE timeline regardless of grade or attribution.

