Both genistein and placebo tablets will be provided by DSM Nutritional Products Europe Ltd, Switzerland.

Other study intervention(s): The chemotherapeutic regimen for each subject will be determined by the treating physician and must contain a combination of at least two agents from the following list during each of the four cycles administered in this study: actinomycin, carboplatin, cisplatin, cyclophosphamide, daunorubicin, doxorubicin, etoposide, ifosfamide, topotecan.

Criteria for evaluation (i.e. endpoints):

Efficacy: To evaluate the effectiveness of genistein administration during myelosuppressive chemotherapy, the following endpoints will be compared between genistein cycles and placebo cycles:

Primary endpoint:

- Duration of grade 4 neutropenia, defined as an absolute neutrophil count (ANC) of < 500 cells/ μ l

Secondary endpoints (per cycle):

- Severity of neutropenia
- Duration of grade 4 neutropenia during hospital admissions for febrile neutropenia
- Frequency and duration of unplanned hospital admissions due to (an) adverse event(s)
- Days with fever (temperature > 101.5° F, or > 100° F more than once in a 24-hour period)
- Incidence and severity of infections
- Duration of antimicrobial agent use
- Duration and severity of oral mucositis
- Duration and severity of peripheral motor neuropathy (in subjects receiving vincristine)
- Incidence and severity of hearing impairment and tinnitus (in subjects receiving a platinum-based chemotherapy agent)
- Number of days delayed and percent reduction of full, planned doses of anti-neoplastic agents due to (an) adverse event(s)
- Incidence of primary and secondary G-CSF use
- Number of required blood product transfusions
- Cytokine, growth factor, C-reactive protein, and homocysteine levels as well as erythrocyte sedimentation rates

Safety: Safety will be assessed by incidence and severity of AEs and changes in physical examinations.

Statistical methods:

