Graphical and repeated measure models will be used to describe the complete pattern of ANC over all four cycles. Between group (e.g. Cycles 1 & 2) and crossover differences (Cycles 1 - 4) form the structure for treatment comparisons. Repeated measure models will be used to assess differences in raw ANC, daily ANC, days with fever, duration of hospitalization, and duration of antimicrobial use for subjects admitted with febrile neutropenia. The Cochran–Mantel–Haenszel test statistics will be used in the analysis of stratified categorical data. The Cochran–Mantel–Haenszel test will be used to compare grade and repeated measure models for duration of mucositis between cycles containing genistein versus placebo. Safety data will be summarized and compared during genistein versus placebo cycles.

TABLE OF CONTENTS

SUMMARY OF CHANGES FROM PREVIOUS VERSION	ii
PROTOCOL SIGNATURE PAGE	iii
STUDY DESIGN SCHEMATIC	iv
SYNOPSIS	v
1 BACKGROUND AND RATIONALE	1
1.1 Study Synopsis	1
1.2 Background	1
1.2.1 Toxicities Associated With Chemotherapy for Pediatric Cancers	1
1.2.2 Anti-cancer/Anti-Inflammatory Effects of Soy Isoflavones	2
1.2.3 Genistein Reduces Chemotherapy-Induced Side Effects	3
1.3 Study Design and Rationale	4
2 STUDY OBJECTIVES	6
2.1 Primary Objectives	6
2.1.1 To estimate the effect of supplementation with genistein on the time to neutrophil count recovery following myelosuppressive chemotherapy	6
2.2 Secondary Objectives	6
2.2.1 To estimate the effect of supplementation with genistein on short-term side effects of myelosuppressive chemotherapy	6
2.2.2 To estimate levels of the serum markers of inflammation during cycles of chemotherapy given in conjunction with genistein supplementation versus placebo	6
3 SUBJECT ELIGIBILITY	7
3.1 Inclusion Criteria	7
3.2 Exclusion Criteria	8
3.3 Enrollment Exceptions	8
4 TREATMENT PLAN	9
4.1 Subject Status Definitions	9
4.2 Recruitment	10
4.3 Informed Consent	10
4.4 Registration	10
4.5 Randomization or Arm Assignment	11
4.6 Unblinding	11
4.7 Dosage and Administration	11
4.7.1 Chemotherapeutic Regimen	11
4.7.2 Genistein/Placebo Supplementation	11
4.7.3 Treatment Delays	12

4.7.4	Dose Modifications	12
4.8	Concomitant Medications/Treatments	13
4.8.1	Prohibited Medications	13
4.8.2	Concomitant Medications	14
4.9	Discontinuation of Protocol Therapy	14
4.10	Withdrawal from Study	15
5	SUPPLEMENT INFORMATION	16
5.1	Genistein	16
5.1.1	Chemical Name	16
5.1.2	Other Names	16
5.1.3	Classification	16
5.1.4	Molecular Formula	16

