9.2.3 Additional reporting Requirements

9.2.3.1 Target Adverse Events

Target AEs are AEs of special interest and will be collected throughout the treatment phase, regardless of expectedness, severity, or attribution. They are listed in [Section 6.3](#). Target AEs will not be collected during the follow-up reporting periods unless the AEs otherwise meet the DSMC or IRB reporting requirements outlined in [Sections 9.2.1](#) and [9.2.2](#).

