9.2.3.3 Reporting to the FDA

The Study Chair or designee is responsible for providing safety updates to the FDA per the following guidelines. The reporting times refer to the time the study team received knowledge of the AE.

Table 9. FDA Reporting Requirements

UVa PI HELD IND			
Type of Event	To whom will it be reported:	Time Frame for Reporting	How reported?
Life-threatening and/or fatal unexpected events related or possibly related to the use of the investigational agent.*	FDA	Within 7 calendar days of the study team learning of the event	Form FDA 3500A (MedWatch) or narrative
Serious, unexpected and related or possibly related AEs*	FDA	Within 15 calendar days after the study team receives knowledge of the event	Form FDA 3500A (MedWatch) or narrative
All AEs	FDA	Annually	IND annual report

*Applies to AEs/SAEs not identified in [Appendix C](#)

Certain anticipated SAEs will not be reported individually to the FDA in an expedited fashion due to their frequency in the study population independent of study supplement exposure. The events listed in [Appendix C](#) are common in patients receiving the chemotherapeutic agents listed in [Section 3.1](#) and so will instead be reported in aggregate to the FDA using an IND safety report should analysis indicate that the toxicities are occurring more frequently in patients taking genistein.

The Study Chair may also choose to refrain from single-event IND safety reporting should an AE/SAE be related to the subject’s underlying disease. These events are not included in [Appendix C](#) due to the wide range of cancers that may participate in this study. As above, such AE/SAEs will be reported using an IND safety report should aggregate analysis demonstrate increased toxicity associated with genistein treatment.

Single-event IND safety reports submitted to the FDA will be blinded, per permission granted by the agency on 19May2017.

Annual reports to the FDA will include AEs and SAEs collected as described in [Section 9.2.1](#), with the exception of target AEs collected solely for the purposes endpoint analysis. Those target AEs are non-serious grades 1 and 2, any attribution to the study supplement, and non-serious grade 3 with an unrelated or unlikely relationship to the study supplement.

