10.1 Data Collection/CRF Completion

All data must be entered into OnCore in accordance the University of Virginia Cancer Center OnCore standard operating procedure (SOP), which can be found on the OnCore Resources page (see the OnCore Help tab). AEs must be entered into OnCore as described in [Section 9.2](#) and in the Procedure Manual. All other study specific data must be entered into OnCore in the timeframes specified in the SOP. Sample CRFs are available in the Procedure Manual appendices.

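### Table 5 does not require database entry of non-target, non-serious grade 3 AEs judged unrelated (by inference, also unlikely), so the planned genistein-versus-placebo AE comparison loses sensitivity there

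*Combined protocol and SAP*

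**What the plan says.** **Safety endpoint.** The Synopsis states: "Safety will be assessed by incidence and severity of AEs and changes in physical examinations." Its statistical paragraph adds: "Safety data will be summarized and compared during genistein versus placebo cycles." Neither sentence restricts the comparison to events thought to be related to the supplement.

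**Entry rule.** Section 10.1: "AEs must be entered into OnCore as described in" Section 9.2 and the Procedure Manual. Within Section 9.2.1, Table 5 is captioned "DSMC reporting requirements for AEs that occur during Cycles" 1–4. It splits grade 3 into target AEs, which are entered, and *All other*. The *All other* column reads *Not required* at the unrelated end and calls for OnCore entry at the related end.

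**Exempt from the filter.** Section 9.2.3.1 collects target AEs during treatment "regardless of expectedness, severity, or attribution". A Table 5 footnote covers SAEs: "Any AE that is an SAE must be reported using the SAE timeline regardless of grade or attribution." Unexpected grade 4 AEs are entered at every attribution level.

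**Who judges.** The investigator assigns attribution (Section 9.1.10). The study team is blinded, apart from the site investigational pharmacist or designee (Section 4.6).

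**Text that points the other way.** Section 9.2.1 opens by requiring every AE to be reported into OnCore, and describes the table thresholds as additional to routine data capture. Section 9 requires all AEs to be recorded in the medical and study records.

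**The concern.** In a randomised, blinded comparison, a supplement effect on AE rates can be seen without anyone having to decide the cause of a single event. That works only if events are recorded before causality is judged.

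Here the background is myelosuppressive chemotherapy. Appendix C lists vomiting, hepatotoxicity, nephrotoxicity and several electrolyte disturbances as toxicities of the chemotherapy agents. None of these is a target AE. An investigator who sees a non-serious grade 3 event of this kind has a ready explanation other than the tablet, and Table 5 then does not ask for it to be entered. If genistein raised the rate of such events, the excess could be thinned to a few records along with the background.

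There is also an asymmetry. Section 6.2.1 requires non-target baseline conditions of grade 3 or higher to be reported, whereas a grade 3 condition arising on treatment need not be entered unless it is attributed to the supplement.

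**Working it through.** The documents give no AE rates, so there is no plan figure to reproduce. The power statement in Section 8.2 concerns ANC recovery and does not bear on this point. The check is mainly a reading of the passages together.

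**1. Where the cut falls.** Row alignment in Table 5 is uncertain in the copy read: *Unlikely* appears beside a 30-day entry. Three other places settle the likely reading.
- Table 6 (follow-up) groups unrelated and unlikely grade 3 AEs as *Not required*. For possible, probable and definite it reads "OnCore: 30 days from end of Reporting" Period. Table 5 uses parallel 30-day and 15-day entries.
- Section 9.2.3.3 bases FDA annual reports on AEs collected under Section 9.2.1, minus target AEs held only for endpoint analysis. Those are non-serious grades 1 and 2 at any attribution, and "non-serious grade 3 with an unrelated or unlikely relationship to the study supplement". A non-target AE of the same description is therefore below the general threshold.
- Section 9.2.3.1 would not need to exempt target AEs from attribution if all AEs were entered anyway.

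So unrelated is *Not required* on the face of Table 5, and unlikely by inference. If unlikely events were in fact entered, the filter would still apply to unrelated ones.

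**2. Whether another rule recovers the events.**
- Section 6.3 requires AEs that trigger a supplement dose reduction to be reported even below the threshold. Section 4.7.4 allows dose changes only for AEs at least possibly related, so this exception also depends on attribution.
- Section 6.3 requires creatinine, bilirubin, AST and ALT on Day 1 of each cycle. It requires all ANC values and raw CRP, homocysteine and ESR data to be reported, but says nothing similar for the chemistry results.
- Section 6.2.1 makes new abnormal findings reportable only if they meet the Section 9 criteria.

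No passage clearly requires database entry of these events.

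**3. What a blinded filter does (assumed rates).** Let p0 and p1 be the shares of placebo and genistein subjects with such an event, and q the share judged possible or higher, assumed equal under both treatments.

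Recorded shares are q·p0 and q·p1. The ratio stays p1/p0, and the difference shrinks to q(p1 − p0).

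Take 22 subjects per group (Section 8.2), a between-group comparison and two-sided 5%. Power = Φ[(d − 1.96·se0)/se1], where d is the recorded difference, se0 = √(p̄(1 − p̄)·2/22), p̄ is the mean of the two recorded shares, and se1 is the unpooled standard error.

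For 30% vs 60%, all recorded: p̄ = 0.45, se0 = 0.150, se1 = 0.143. Power = Φ[(0.30 − 0.294)/0.143] = Φ(0.04) = 52%.

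For the same rates with q = 0.10: recorded shares 3% and 6%, se0 = 0.0625, se1 = 0.0623. Power = Φ[(0.03 − 0.1225)/0.0623] = Φ(−1.48) = 7%. Expected recorded subjects are 22 × 0.03 = 0.7 and 22 × 0.06 = 1.3.

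| Assumed true rates | All recorded | q = 0.50 | q = 0.25 | q = 0.10 | q = 0.05 |
|---|---|---|---|---|---|
| 20% vs 40% | 30% | 15% | 9% | 6% | 5% |
| 30% vs 60% | 52% | 22% | 12% | 7% | 5% |
| 40% vs 70% | 52% | 20% | 11% | 6% | 5% |

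The normal approximation is rough at the smallest counts. The table shows the direction and mechanism of the loss; it does not estimate the loss in this trial.

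**The case against.** The strongest reply is that Table 5 governs expedited or additional DSMC reporting, not the analysis dataset. The opening of Section 9.2.1 supports that, and both Sections 9.2.1 and 10.1 also point to the Procedure Manual, which is not among the documents. A reader might infer from Table 5 that these events never reach the dataset. The documents do not support so firm a statement: *Not required* does not forbid entry, and routine capture may be defined in the manual. What stands is that no available passage defines it, and that the passages conflict.

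Three other strong readings are tempting and also go too far.
- *A rise in liver enzymes on genistein would be invisible.* Chemistry is drawn every cycle under both treatments. Section 6.3 also collects AE-related hospitalisations, chemotherapy delays and dose reductions, so a consequential event may leave a trace. Entry of the chemistry values, however, is not stated.
- *The AE comparison measures only investigator suspicion, or is biased.* Target AEs, SAEs and unexpected grade 4 events escape the filter, and the investigator who assigns attribution is blinded. The loss is one of sensitivity within one category.
- *The gap is confined to non-serious grade 3.* Table 5 also exempts non-target grade 1–2 AEs, apparently at any attribution. These include abdominal pain of grade 2 or lower, the only AE that Section 5.1.7 treats as expected with genistein.

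Finally, limited AE entry is a legitimate economy in a pilot. Section 9.1.1 openly restricts reporting to clinically significant AEs, and Section 8.4 specifies no AE test. That is fair for grades 1–2. It is weaker for grade 3, where the Synopsis still promises a comparison by treatment.

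**Conclusion.** The point holds in limited form. On the operative text, OnCore entry of non-target, non-serious grade 3 AEs in Cycles 1–4 is not required when they are judged unrelated and, by inference from Table 6 and Section 9.2.3.3, unlikely. That is at odds with a safety comparison defined by AE incidence and severity without regard to cause.

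The consequence is fewer recorded events under both treatments and less chance of seeing a real difference, with no built-in tilt toward either arm. The last part assumes that the blinded investigator attributes events alike under both treatments. How much is lost cannot be worked out from the documents, because they give neither the event rate nor the share judged related. Full recording would not make this small trial well powered for safety either: the assumed scenarios reach only 30% to 52%. The reason to change the rule is that the information is cheap to keep and cannot be recovered reliably later.

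**What to change.** 1. In Table 5, Grade 3 *All other*, replace *Not required* for unrelated and unlikely with routine OnCore entry within 30 days of the end of the cycle, for Cycles 1–4.
2. State in Section 8.4 that grade 3 or higher AEs will be compared by treatment regardless of attribution.
3. State that the grade 1–2 comparison covers target AEs only, so that the existing exemption can stay without misleading the reader.
4. Reconcile Section 9, the opening of Section 9.2.1 and Section 10.1, so that one sentence says which AEs enter the database and which set the safety summary uses.

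Cost: more routine AE entry over four cycles in about 50 subjects. No new visits or assessments are needed, because Section 9 already requires these events to be assessed and recorded in the study records.
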